9.6. Follow-Up Visits

Table 3 below specifies permitted time windows for the required subject visits. Subject visit target dates and windows for each follow-up will be made available to the study site. Follow-up visit windows are based on days post-acute MI, and the follow-up visit can be performed either in person or via phone. If a subject visit fall outside the pre-specified window, a study deviation must be reported and the original follow-up schedule maintained for subsequent visits.

Data analyses will include follow-up visits, regardless of whether the visits occur within the time window. Therefore, a late visit is preferred over a missed visit but must be accompanied by a deviation.

Table 3: Follow-up windows

Study Follow-up Visit	Window (Calculated days post-acute MI)		
	Window Start (days post-MI)	Target (days post-MI)	Window End (days post-MI)
3 month	40	90	120
6 month	150	180	210
12 month	335	365	395

Complete a Subject Visit CRF for each follow-up visit.

At 3-month follow-up visit, LVEF will be assessed as per standard practice:

- As per Investigator's discretion, if the subjects have LVEF $\leq 40\%$ or meeting one of the referral criteria (sustained VT, cardiac or unexplained syncope, clinically significant palpitations, new onset bundle branch block, conduction abnormalities, or symptomatic bradycardia), the subjects can be referred for SCD risk stratification and management (EP Referred Group). If the referral does not take place, it is not a study deviation.
- If the subjects have LVEF $>40\%$ but $<50\%$ (between 41% - 49%), the subjects will remain in the Non-Referred Group.
- If the subjects have LVEF $\geq 50\%$, they shall be exited from the study.

For the Non-Referred Group, a Referral Status CRF is needed for each subsequent visit unless the subject is referred to the EP Referred Group. During study follow-up visits, the Non-Referred Group subjects can be referred to the EP Referred Group if their LVEF is $\leq 40\%$ or meets one of the referral criteria (as listed above).

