9.7. Study Exit

At 3-month follow-up, if a subject has an LVEF $\geq 50\%$, the subject will be exited from the study. Subject who remain in the study after 3-month follow-up should remain in the study until the 12-month follow-up is completed or until all data required to meet study objectives have been collected (whichever comes first). Either an in-office visit or phone call is required for study exit.

A study exit eCRF is required for all subjects. Prior to exiting a subject from the study, it is recommended to follow the subject until all AEs are resolved. Following exit, subjects will continue to receive standard medical care. Upon exiting from the study, no further study data will be collected or study visits will occur for the subject. Exited subjects will not be replaced with newly enrolled subjects.

Subjects are urged to remain in the study as long as possible, but may be exited from the study for any of the following situations:

- Study closure
- Subject lost to follow-up (refer to Section 9.11.1)
- Subject did not meet inclusion/exclusion criteria
- Subject did not provide consent or data use protection authorization
- Subject chooses to withdraw (refer to section 9.11.2 for more information)
- Investigator deems withdrawal necessary (e.g. medically justified, inclusion/exclusion criteria not met)
- Subject exited study at the 3 months visit if the 3-month LVEF is $\geq 50\%$
- Subject completed study after 12 months visit
- Subject Death

For study exit visits the following information is required:

- Reason for exit
- Final interrogation file (or CareLink transmission) for subjects implanted with Medtronic device
- Cardiovascular Adverse events, Study Deviations and System Modification

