Figure 1 Study Flow

***For patient enrollment:** Patients must be enrolled ≤ 30 days post-acute MI and must have an $EF < 50\%$ measured ≤ 14 days post-acute MI.

****Referral Criteria:** sustained VT, cardiac or unexplained syncope, clinically significant palpitations, new onset bundle branch block, conduction abnormalities, or symptomatic bradycardia.

Table 1 below specifies the time windows for the required subject visits, which are based on days post-acute MI. If a subject visit falls outside the pre-specified window, a study deviation will be reported, and the original follow-up schedule maintained for subsequent visits.

Data analyses will include follow-up visits, regardless of whether the visits occur within the time window. If a subject has an out of window visit, referral will be counted at the consecutive visit, while non-referral will be counted at the previous visit. For example, if a subject has a 3 months visit at 140 days post MI and is referred, he'll be considered as having been referred at the 6 months visit. On the contrary, if a subject has a 3 months visit at 140 days post MI and is not referred, he'll be considered as not having been referred at the 3 months visit. Rationale of this is:

1. When the late visit does not have the event (e.g. no referral yet), the event also had not happened yet in the window of the previous visit, but it may occur at the consecutive visit.
2. When the late visit has the event (e.g. referral), the status at the next visit is referred, but it is unsure whether the referral would have already happened in the window of the previous visit.

Table 1: Follow-up windows

Study Follow-up Visit	Window (Calculated days post-acute MI)		
	Window Start (days post-MI)	Target (days post-MI)	Window End (days post-MI)
3 month	40	90	120
6 month	150	180	210
12 month	335	365	395

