  table referred/binomial (cl = wilson) alpha = 0.05 out = perc;
  ods output binomialCLs=percConf;
run;
```

The results will be shown for each region and overall in a table similar to the example table below:

Table 3: percentage (95% CI) of subjects referred for sudden cardiac death risk (SCD) stratification and management, among the subjects with at least one reason for referral at the 3 months visit (chronic phase)

Region	Proportion Referred	95% CI
Region 1	XX/XX (XX.XX%)	(XX.XX% - XX.XX%)
Region 2	XX/XX (XX.XX%)	(XX.XX% - XX.XX%)
...
Overall	XX/XX (XX.XX%)	(XX.XX% - XX.XX%)

A subject not referred for SCD risk stratification and management during their three months visit may later be referred. Thus, similar descriptive statistics may be generated at the 6 and at the 12 months post-baseline visits and displayed in a table similar to table 2 above.

Further, as part of an attempt to continually train the physicians on referring subjects with a reason for referral, periodic feedbacks on referral rates will be provided. Whether these periodic feedbacks will have an impact on referral rate will be investigated by producing, for each region and overall and over time, a penalized B spline plot. A SAS code similar to the below will be used:

```
ods graphics on / attrpriority=none;
proc sgplot data=referral noautolegend;
  title 'Penalized B-Spline for each region';
  styleatrrs datalinepatterns=(solid);
  pbspline y=prop x=time/group=region;
run;
```

Additional analyses may be provided and described in the final report.

Additionally to the analyses described above, logistic regression models might be used overall and by region, to estimate the odds ratios of referring patients for SCD stratification and management

depending on different factors, such as age, gender, LVEF≤40% versus any other reason for referral, physician's specialty, PCI versus non-PCI patients, STEMI versus non-STEMI patients. An example SAS code similar to the below will be used:

```
proc logistic data = referral;
  by region;
  class factor/descending;
  model referred (event = '1') = factor/expb;
  oddsratio factor;
  ods output ParameterEstimates = ParEstim;
  ods output OddsRatiosWald = OREstim;
run;
```

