- (c) Having had an SCD stratification visit;
- (d) Having been indicated an ICD/CRT-D implant
- (e) Having received an ICD/CRT-D.

An SAS code for the competing risk analysis similar to the below will be used:

```
proc lifetest data=KM plots=cif(test) timelist=0 1 2 3 4 5 6 7 8 9 10 11 12;
  by region;
  time T*Status(0) /eventcode=1;
  strata Event / order=internal;
run;
```

where Event is a categorical variable with categories the event of interest (meeting the referral criteria, having been referred, having had an SCD risk stratification visit, having been indicated for an ICD/SCD-D implanted, having received an ICD/CRT-D), T is the time in months from enrollment to the date of the event of interest and Status is an indicator variable with 3 values: 0 for censored observations, 1 observations related to the event of interest and 2 observations related to subjects who died. Note that the dataset to be used will contain one row for each event per subject (e.g.: if a subject will have all events, from having met the referral criteria to having received the ICD/CRT-D, the dataset will contain 5 rows for that subject).

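### The SAP 5.1 out-of-window rule counts late-recorded referrals and late non-referrals differently, and gives a referral first recorded after day 395 no visit at which to be counted

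*SAP*

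**What the plan says.** SAP 5.1, in the text above Table 1, includes all follow-up visits in the analyses whether or not they fall in the window. It then says how an out-of-window visit is counted: "referral will be counted at the consecutive visit, while non-referral will be counted at the previous visit". Both worked examples concern a 3-month visit held on day 140. If the subject is referred, he is to "be considered as having been referred at the 6 months visit"; if not, he is to "be considered as not having been referred at the 3 months visit". The reasoning given refers to late visits and to an event, with referral as the example.

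The last row of SAP Table 1 reads "12 month 335 365 395" (start, target and end, in days after the MI). Protocol 9.7 lists among the reasons for exit "Subject completed study after 12 months visit". Protocol 9.6 says that "a late visit is preferred over a missed visit", so late visits are expected.

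For referral after month 3, SAP 7.9.1.3 says that "similar descriptive statistics may be generated at the 6 and at the 12 months post-baseline visits". The competing-risk curves in SAP 7.9.3.3 do not use visit slots: "T is the time in months from enrollment to the date of the event of interest".

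**The concern.** The rule needs a later visit to receive a late-recorded referral. At month 12 there is none, and no exception is written for the last visit. A late non-referral needs no later visit and stays at month 12. Any loss therefore runs in one direction: events can disappear from the month-12 count and non-events cannot.

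The rule also tests the wrong date. A referral made between the 6-month and 12-month windows is normally first recorded at the 12-month visit. If that visit is late, the referral has no slot, although it was made in time.

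The study's results are descriptive proportions by region. A one-directional counting rule affects them directly, and by different amounts if visit timeliness differs between regions.

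**Working it through.** **The plan's own figure.** The plan states no rate of late visits. The nearest stated figure is the sample size in SAP 6.1, which reproduces. With a Wilson 95% interval, half-width 0.125 and proportion 0.70, the probability of reaching the target is 0.784 at n = 53 and 0.897 at n = 54. Then 54/0.30 = 180 and 180/0.90 = 200. None of this depends on the out-of-window rule.

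**The rule applied to each row of SAP Table 1.**

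| Visit (window end) | Late, referred: counted at | Late, not referred: counted at |
|---|---|---|
| 3 month (day 120) | month 6 | month 3 |
| 6 month (day 210) | month 12 | month 6 |
| 12 month (day 395) | no later row | month 12 |

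**Cases, by the rule and by event date.**

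- 12-month visit on day 400, referral made on day 300. Rule: no slot. By date: referred at month 12.
- 12-month visit on day 400, referral made that day. Rule: no slot. By date: after the limit, so not yet reached at month 12, with the subject kept in the denominator.
- 12-month visit on day 400, no referral. Both: not referred at month 12.
- 3-month visit on day 140, referral dated on or before day 120. Rule: month 6. By date: month 3.
- 3-month visit on day 140, referral made that day. Both: month 6.

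The two methods give different counts for an event dated within the window but recorded late.

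**Size at month 12 (all inputs assumed).** Let p be the true proportion with an event dated within the limit, m the part of p first recorded at the 12-month visit (m ≤ p), and L the share of 12-month visits after day 395, taken as unrelated to the event. The SAP does not say whether an uncounted subject stays in the denominator.

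- Kept in the denominator: reported = p − mL.
- Removed: reported = (p − mL)/(1 − mL).

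The loss is greatest at m = p, where these become p(1 − L) and p(1 − L)/(1 − pL). For p = 20%:

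| L | m = p, kept | m = p, removed | m = 5 points, kept |
|---|---|---|---|
| 5% | 19.0% | 19.2% | 19.75% |
| 15% | 17.0% | 17.5% | 19.25% |
| 30% | 14.0% | 14.9% | 18.5% |

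For L = 15%: 0.20 × 0.15 = 3 points at most, against 0.05 × 0.15 = 0.75 points when only 5 points are new at that visit.

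**Size at month 3.** Take the SAP's planning value of 70% referred among 54 subjects with a reason for referral, and let L now be the share of 3-month visits after day 120. At most 54 × 0.70 × L referrals move to month 6: 1.89, 3.78 and 7.56 for L = 5%, 10% and 20%. The reported 70% becomes 66.5%, 63.0% and 56.0% if the subject is kept, or 68.9%, 67.7% and 65.1% if removed. These are also limiting values. A referral decided at the late visit carries a date after day 120 and belongs after month 3 in any case.

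**The case against.** The best defence is that the plan nowhere says such referrals are dropped. The sentence just before the rule includes every visit regardless of window. Protocol Table 2 collects referral and implant status at study exit, and Protocol 9.7 requires an exit form for every subject. This stands as far as it goes: a reader might infer that the SAP discards late month-12 referrals, but it is silent on them. The inclusion sentence, however, names no time point for them, and the SAP defines no exit time point in its visit-level tables.

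Second, the reach is narrow. The month-12 referral proportion is optional. The month-12 summary that SAP 7.9.1.3 does require repeats Table 2, which groups subjects by whether they had a reason for referral, not by whether they were referred. A reader might infer that secondary objectives 1 and 2 are biased as written. The documents do not support that: the rule is spelled out only for referral, and the indication and implant tables (SAP Tables 5 and 6) are built from CRF answers. They are exposed only if a programmer takes the rationale's general term, event, to cover them. The curves use event dates and already give date-based cumulative results to 12 months from enrollment.

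Third, an event after day 395 may lie outside a 12-month objective, so leaving it out is defensible. That is right for events dated after the limit. It does not cover an event dated earlier and recorded late, because the rule never looks at the event's date.

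A reader might also infer a mirror-image loss of non-referrals at early 3-month visits. Both parts of the rationale and both examples concern late visits, so the text does not support that extension.

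**Conclusion.** The point holds in limited form. The rule is asymmetric and has no destination for a referral first recorded at a 12-month visit after day 395. Applied literally, it biases the optional visit-level month-12 referral proportion downward. Effects on the indication and implant tables are conditional on extending the rule to them; the curves and the sample size are unaffected.

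The month-3 counterpart deserves equal attention, because the primary proportion is computed there: a late-recorded referral moves to month 6 while a late non-referral stays at month 3.

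The size is unknown. The loss is confined to events first recorded at a late visit but dated within its limit. The p(1 − L) values show the largest loss on the assumption that lateness is unrelated to the event, and should not be read as an estimate. The late shares are not in the documents. The gap should be closed before analysis, but it does not threaten the study's main conclusions as planned.

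**What to change.** In SAP 5.1, replace the out-of-window rule with classification by the event's own date:

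- Count an event at a visit if it is dated on or before that visit's stated limit, whatever the date of the visit that reported it. The window ends in Table 1 are days 120, 210 and 395. For month 12 the sponsor should state whether the limit is day 395 or, if that is how it defines 12 months, day 365.
- Treat an event dated later as not yet reached at that visit, and keep the subject in the denominator.
- Say whether the rule covers indication and implant as well as referral.
- Count days from the MI, as Table 1 does. The time variable in SAP 7.9.3.3 runs from enrollment, which may be up to 30 days after the MI.

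The cost is one SAP paragraph and a programming change. No new data should be needed, since SAP 7.9.3.3 already requires the event dates. The case report forms are not among the documents, so the sponsor should confirm that they record those dates.

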5.2. Duration

The study duration is expected to be approximately 24 months. The first enrollment occurred in Nov 2018. The 24 months study duration represents an estimated 12 months for subject enrollment and 12 months for subject follow-up for the last subject enrolled. At approximately 12 months past the final study enrollment, centers will be notified that study closure is about to occur.

5.3. Rationale

This study is characterizing care pathway of post MI patients and understanding the evolution of LVEF for post MI patients, which will improve the management of this group of patients in prevention of SCD.

5.4. Study Population

Patients of both genders who have had an acute MI \leq 30 days of enrollment and have a LVEF $<50\%$ measurement \leq 14 days post-MI will be approached regarding enrollment in the study. Patients implanted with ICDs or CRT-Ds or have had an EP referral in the last 12 months will not be approached for this study.

5.5. Eligibility

5.5.1. Inclusion Criteria

The inclusion criteria are as follows:

- Age 18 and above (or meet age requirements per local law)
- Patients who have an acute Myocardial Infarction (MI)* (STEMI or non-STEMI) \leq 30 days of study enrollment and have a LVEF $<50\%$ measurement \leq 14 days post- MI
- Willing and able to give informed consent

* Strongly recommend following the ESC guideline for acute MI definition.

5.5.2. Exclusion Criteria

The exclusion criteria are as follows:

- Patient has previously received or currently implanted with an ICD or CRT-D
- Patient has any contraindication for ICD/CRT-D
- Patient's life expectancy of less than 12 months
- Patient who has had an EP referral within the last 12 months
- Any exclusion criteria required by local law (e.g. pregnancy or breast feeding etc.)
- Patient is unable (e.g. mental disorder) or unwilling to be compliant with the responsibilities as specified in the informed consent form.
- Patient is enrolled in a concurrent study that has not been approved for concurrent enrollment by the Medtronic Clinical Trial Leader*

**Concurrent enrollment with observational registry is allowed without approval from the Medtronic Clinical Trial Leader if the Principal Investigator confirms that the registry has no intervention beyond standard of care and may not confound study results prior to enrollment.*

6. Determination of Sample Size

6.1 Sample Size Assessment

The sample size calculation was based on the width of the 95% confidence interval for the proportion of subjects that is referred for SCD risk stratification and management among subjects who have a reason for referral at the 3 months visit. The following assumptions were made:

- Drop-out and mortality rate combined from enrollment to 3 months visit of 10%,
- At the 3 months visit, 30% of subjects will have a reason for referral.

Under these assumptions, enrollment of approximately 200 patients per region is needed, to have at least 80% power to achieve a 95% confidence interval width of 25% when 70% of patients with a reason for referral at the 3 months visit is referred for SCD risk stratification and management.

The sample size has been computed as follows.

First, the number of subjects needed in each region with a reason for referral at the 3 months visit ($N_{\text{reason_referral}}$) was computed using the SAS procedure below:

```
proc power;
onesamplefreq
  ci = wilson
  halfwidth = 0.125
  probwidth = .
  proportion = 0.70
  ntotal = 40 to 70 by 1;
run;
```

where proportion = 0.70 is the proportion of subjects to be referred among those with a reason for referral and halfwidth = 0.125 is half of the 95% confidence interval around this proportion. As a result of the above SAS procedure, the needed number of subjects that will give at least 80% power to achieve a 95% confidence interval of halfwidth = 0.125 around a proportion of 70% of subjects with a reason for referral that will be referred is $N_{\text{reason_referral}} = 54$.

Secondly, the number of subjects expected at the 3 months visit was computed as the ratio between the required number of subjects with a reason for referral at the three months visit ($N_{\text{reason_referral}} = 54$) and the assumed proportion of subjects with a reason for referral at the three months visit ($\text{prop}_{\text{referral_assumed}} = 0.30$) :

$$N_{\text{3months}} = \frac{N_{\text{reason_referral}}}{\text{prop}_{\text{referral_assumed}}} = \frac{54}{0.30} = 180$$

The number of subjects to be enrolled was then computed as the expected number of subjects that will complete the three months visit ($N_{\text{3months}} = 180$) and the assumed proportion of subjects that will not drop-out or die between enrollment and the 3 months visit ($1 - \text{rate}_{\text{exit_assumed}} = 0.90$):

$$N_{\text{enrolled_planned}} = \frac{N_{\text{3months}}}{1 - \text{rate}_{\text{exit_assumed}}} = \frac{180}{0.90} = 200$$

Therefore, assuming a drop-out and mortality rate of 10% and a proportion of subjects with a reason for referral of 30%, approximately 200 subjects needs to be enrolled in each region to ensure at least a 80% power to achieve a 95% confidence interval width of 25% when 70% of patients with a reason for referral at the three months visit will be referred.

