6.2 Sample Size Re-assessment

Drop out and mortality rates from enrollment to the 3 months visit and the proportion of subjects with a reason for referral at the 3 months visit will be monitored on an ongoing basis to account for possible heterogeneity in the drop-out and mortality rate and in the proportion of subjects with a reason for referral across geographies. A sample size re-assessment may be performed in regions with mortality

and drop-out rates different than 10% or with a proportion of subjects with reasons for referral different than 30%. The sample size reassessment will be produced as explained below.

The data gathered from each region at the time of the sample size re-assessment from enrollment to the 3 months visit will be used to compute the observed mortality and drop-out rate at the 3 months visit ($rate_{exit_observed}$) and the proportion of subjects with a reason for referral at the 3 months visit ($prop_{referral_reason}$) as follows:

$$rate_{exit_observed} = \frac{\text{Number of deaths and drop out before the 3 months visit}}{\text{Number of subjects enrolled}}$$

$$prop_{referral_reason} = \frac{\text{Number of subjects with a reason for referral at the 3 months visit}}{\text{Number of subjects with a 3 months visit completed}}$$

In regions where the drop-out and mortality rate ($rate_{exit_observed}$) will differ from 10% or the proportion of subjects with a reason for referral ($prop_{referral_reason}$) will differ from 30%, the total number of subjects to be enrolled ($N_{enrolled}$) will be computed following the below two steps:

Step 1: the number of subjects expected at the 3 months visit, given $prop_{referral_reason}$ will be computed as the ratio between the required number of subjects with a reason for referral at the three months visit ($N_{reason_referral} = 54$) and the observed proportion of subjects with a reason for referral at the three months visit ($prop_{referral_reason}$):

$$N_{3months} = \frac{54}{prop_{referral_reason}}$$

Step 2: the number of subjects to be enrolled, given $rate_{exit_observed}$ will be computed as the expected number of subjects that will complete the three months visit and the observed proportion of subjects that did not drop-out or die between enrollment and the 3 months visit ($1 - rate_{exit_observed}$):

$$N_{enrolled_update} = \frac{N_{3months}}{1 - rate_{exit_observed}}$$

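### A fixed 200 enrolled per region meets the planned interval width with probability about 76%, not at least 80%, and the SAP 6.2 exit rate is biased low while enrolment is running

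*SAP*

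**What the plan says.** SAP 6.1 first finds that 54 subjects with a reason for referral give at least 80% probability that the Wilson 95% interval has a half-width of 0.125 or less when 70% are referred. It then works back to enrolment: "the number of subjects expected at the 3 months visit was computed as the ratio between the required number of subjects" (the 54) and the assumed 30%, giving 180. Dividing by 0.90 gives 200. The section closes by saying that "approximately 200 subjects needs to be enrolled in each region to ensure at least a 80% power to achieve a 95% confidence interval width" (target 25%). Protocol 12.2.5 attaches the same probability to about 200 enrolled.

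SAP 6.2 adds a regional update. Exit rates and reasons for referral "will be monitored on an ongoing basis to account for possible heterogeneity in the drop-out and mortality rate" and in the share with a reason. The update is optional: "A sample size re-assessment may be performed in regions with mortality" and drop-out other than 10%, or a share with a reason other than 30%. On inputs it says "The data gathered from each region at the time of the sample size re-assessment from enrollment to the 3 months visit will be used". The exit rate is "Number of deaths and drop out before the 3 months visit" divided by "Number of subjects enrolled". The share with a reason for referral is instead divided by "Number of subjects with a 3 months visit completed". The new target is 54 divided by the observed share and by one minus the observed exit rate. SAP 6.2 ends by repeating the 80% guarantee for the updated number.

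SAP 6.2 describes the number as changing from about 200, without giving a direction. Protocol 6 describes an increase to at most 2,400 in total. Protocol 12.4 describes continuing past 200 in some geographies and stopping at about 200 in others.

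**The concern.** There are three linked problems.

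1. The 80% in SAP 6.1 is a property of 54 subjects with a reason for referral, but it is claimed for 200 enrolled. The step between the two uses an average, and the probability of meeting the width drops quickly once the realised count is below 54.
2. The SAP 6.2 exit rate counts recently enrolled subjects in full in the denominator, although they have not had their full time to die or drop out. No maturity cut-off is given. The rate is too low during enrolment whatever the accrual pattern, and that is when a re-assessment is useful. The two inputs to the update also come from different cohorts.
3. SAP 6.2 promises at least 80% after the update. What is achieved depends on when the re-assessment is done, on the true exit rate, and on whether a target may fall below 200, which the documents do not settle.

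The stake is a wider interval for the primary proportion in some regions. No hypothesis test is involved. The second problem matters most, because it under-corrects in regions with high death or drop-out, which are the regions the re-assessment is meant to serve.

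**Working it through.** **Inputs.** From SAP 6.1: Wilson 95% interval, half-width 0.125, 70% referred, 10% exit before 3 months, 30% with a reason for referral. From SAP 5.2: 12 months of enrolment.

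**Reproducing the plan.** For x referred out of n, with p = x/n and z = 1.96, the Wilson half-width is z/(1 + z²/n) × √[p(1−p)/n + z²/(4n²)]. Summing Binomial(n, 0.70) probabilities over all x with half-width at most 0.125:

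- n = 50: 56.9%
- n = 52: 72.2%
- n = 53: 78.4%
- n = 54: 89.7%
- n = 55: 92.7%

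So 54 is the first n reaching 80%, and 54/0.30 = 180, 180/0.90 = 200. The plan's figures reproduce exactly.

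**Fixed 200 enrolled.** Each enrolled subject stays and has a reason with probability 0.90 × 0.30 = 0.27, so the count M is Binomial(200, 0.27) with mean 54. P(M < 54) = 47.3%. Averaging the probabilities above over M:

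- 200 enrolled: 76.25%
- 203: 79.2%
- 204: 80.1%
- 210: 85.2%

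Holding the number at 3 months at exactly 180 still gives only 76.5%. The expected interval width at 200 enrolled is 23.6%.

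**Exit-rate bias.** The documents give neither accrual pattern nor exit timing. Assume uniform accrual and exits spread evenly over the 3 months after enrolment. At month t of accrual, a fraction (t−3)/t has full follow-up and 3/t has on average half of it. The expected observed rate is therefore the true rate × (t − 1.5)/t: 75% of it at month 6, 83% at month 9 and 87.5% at month 12. A true 20% reads as 15.0%, 16.7% or 17.5%. At month 6, with 30% having a reason, the target is 180/0.85 = 212 instead of 180/0.80 = 225.

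**Simulation of SAP 6.2.** Further assumptions: 200 accrued over 12 months, 30% with a reason, one re-assessment at month 6, 9 or 12, and observed subjects kept in the final sample. There were 40,000 runs per cell. Entries are the probability of a width of 25% or less at months 6/9/12.

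| Reductions below 200 | True exit rate | Formula as written | Exit rate from mature subjects |
|---|---|---|---|
| Not allowed | 10% | 89/90/91% | 90/91/92% |
| Not allowed | 20% | 76/78/81% | 81/83/86% |
| Not allowed | 25% | 69/72/76% | 77/80/84% |
| Allowed | 10% | 70/77/91% | 74/81/92% |
| Allowed | 20% | 64/71/81% | 73/79/86% |
| Allowed | 25% | 61/68/76% | 72/78/84% |

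Even with a mature exit rate, the result runs from about 72% to 92%. Whether reductions are allowed moves it by up to 0.889 − 0.697 = 19 points (formula as written, true 10%, month 6).

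**Sensitivity, no reductions (20,000 runs per cell, cap of 400 per region).** If the visit falls 2 months after enrolment, 20% exit gives 78–83% as written against 82–87%, and 25% gives 72–79% against 78–85%. If half the exits fall in the first month, the figures are 77–82% against 81–86%, and 70–78% against 77–84%.

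**The case against.** The strongest reply is that SAP 6.1 follows a common planning convention. Taking 10% and 30% as fixed, 200 enrolled gives exactly 54, where the probability is 89.7%. Every statement says approximately 200, and 204 is arguably within that. The shortfall also hangs on a hard threshold: a fixed 200 gives 84.5% for a width of 25.5% and 89.6% for 26%. If the re-assessment is done and targets cannot fall below 200, the formula as written gives 89–91% at the planned exit rate. This shows that the first point is small. It does not rescue the claim, because the count with a reason for referral is not fixed and the re-assessment is optional.

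On SAP 6.2, the wording "The data gathered from each region at the time of the sample size re-assessment from enrollment to the 3 months visit will be used" could be read as limiting the data to matured subjects. But the printed denominator is "Number of subjects enrolled" without restriction, and it would govern the programming.

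On size, the losses appear at exit rates of 20–25%, at least double the plan's 10%, and no document predicts such rates. Visits are timed from the MI and enrolment can be up to day 30, so 3 months of exposure is the long end for an on-target visit. Combining a 2-month visit with 60% of exits in the first month gives 78/81/84% against 82/84/87% at 20% exit. Correcting the rate changes mean interval width by only 0.3–0.4 percentage points at 20% exit and 0.4–0.65 at 25%, and mean width stays below 24%. Repeated later looks would also shrink the bias. All of this stands as a limit on importance, but the direction of the bias does not depend on it.

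Finally, Protocol 12.4 also says heterogeneity may call for a different number of patients. That is too general to settle whether a target may go below 200.

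**Conclusion.** The point holds. For a fixed 200 enrolled under the plan's own rates, the probability of a 25% width is about 76%; this needs only that those rates be treated as probabilities. The gap is four subjects per region. The SAP 6.2 exit rate is biased low during enrolment on its printed definition. At a true exit rate of 20–25% with no reduction below 200, it costs about 5 to 8 percentage points in the base case; at 10% it costs almost nothing. Those magnitudes rest on assumed accrual, exit timing and exit rates. The SAP 6.2 guarantee of at least 80% is not generally met, even with a correct exit rate. The consequence is lower precision of a descriptive estimate in some regions. It is worth correcting because the correction is cheap, but it does not threaten the study.

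**What to change.** - In SAP 6.1 and Protocol 12.2.5, state that 200 enrolled gives a probability of about 76% and that 204 gives 80%.
- In SAP 6.2, compute the exit rate only among subjects whose 3-month window (day 120 post-MI) has closed, or by Kaplan-Meier. Take the share with a reason for referral from the same cohort.
- At the end of SAP 6.2, present the 80% as an aim, because what is achieved depends on the timing of the re-assessment.
- State whether a regional target may fall below 200, so that SAP 6.2 and Protocol 12.4 agree.

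The cost is wording and one denominator. Restating SAP 6.1 needs no extra patients; holding 80% at a fixed size needs 4 more per region. With no reductions, the corrected exit rate raises the average simulated regional target by 1–3 subjects at a true 10% exit, 6–12 at 20% and 9–16 at 25%. The largest average target was 264, and 6 × 264 = 1,584 is well within the 2,400 maximum.
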